## Version control log

Version Number	Date	Summary of changes
1.2	05/07/2021	

**List of abbreviations and definitions**

Abbreviation	Term
TLC	Therapies for Long COVID
PROs	Patient Reported Outcomes
CPRD	Clinical Practice Research Datalink
WP	Work Package
PPIE	Patient and Public Involvement and Engagement
HES	Linked Hospital Episode Statistics
UK-CIC	UKRI funded Coronavirus Immunology Consortium
NIHR	National Institute for Health Research
IRSP	Intervention Research Service Platform
CHESS	PHE COVID-19 Hospitalisations in England Surveillance System
PID	Patient Identifiable Data
GCP	Good Clinical Practice
PPE	Personal Protective Equipment
EQ-5D 5L	EuroQol-5D 5 level
FACIT-Fatigue	The Functional Assessment of Chronic Illness Therapy – Fatigue Scale
GAD-2	Generalised Anxiety Disorder -2
PCL-2	Abbreviated Post Traumatic Stress Disorder Checklist – Civilian version
PHQ-2	Patient Health Questionnaire -2
GP	General Practice
SBQ-LC™	Symptom Burden Questionnaire for Long COVID
SARS CoV-2	Severe Acute Respiratory Syndrome Coronavirus 2

**STUDY SUMMARY**

Study Title	Therapies for Long COVID in non-hospitalised individuals: From symptoms, patient reported outcomes and immunology to targeted therapies (The TLC Study)
Short Title	Therapies for Long COVID in non-hospitalised individuals (TLC Study)
Study Design	Population based cohort
Study Participants	
Non-hospitalised individuals with a diagnosis of COVID-19 and symptoms lasting at least 12 weeks (“Long COVID”).
 
Matched control patients: i) individuals without a diagnosis of COVID-19; ii) individuals with a diagnosis of COVID-19 but without long-term symptoms.
 
Co-production workshops: Patients and their family members, healthcare professionals, experts in relevant symptoms and corresponding interventions, regulators, and policymakers (NICE).

Planned Size of Sample	
Minimum of 2000 individuals with a diagnosis of COVID-19.
 
Minimum of 500 individuals with Long COVID identified from the main cohort of individuals with COVID-19.
 
Minimum of 500 matched control patients without a diagnosis of COVID-19.
 
Minimum of 500 matched control patients with a diagnosis of COVID-19 but without long-term symptoms (i.e., without Long COVID).
 
Up to 200 individuals from the Long COVID cohort, 50 matched control patients without COVID-19, and 50 individuals with COVID-19 but without long-term symptoms, selected for bio-sampling (sample clusters) and wearables.
 
Co-production workshops: Approximately 40 stakeholders including patients and their family members, healthcare professionals, experts in relevant symptoms and corresponding interventions, regulators, and policymakers (NICE).

Follow-up duration	Monthly for 12 months
Planned Study Period	16 months
Research Question/Aim(s)	
To evaluate the symptom burden and underlying pathophysiology of Long COVID syndromes in non-hospitalised individuals.
 
To co-produce an intervention that can be delivered remotely for supporting individuals with Long COVID syndromes.
 
To gain consensus on therapies to recommend, therapies to evaluate and therapies to recommend against using for the clinical management of Long COVID.

Design and methods	
Work package 1 will identify people that had COVID-19 from GP records. Study participants will be invited to use an app or website to report symptoms, quality of life and work capability.
 
Work package 2 will assess Long COVID symptom burden and define symptom clusters. A sub-cohort will be invited to provide blood and saliva samples to investigate the immune basis for Long COVID and help identify potential therapeutic targets. Wearable devices will be provided to understand the effects of Long COVID on heart rate, oxygen levels, physical activity and sleep.

	
Work package 3 will draw upon existing evidence for treatments for Long COVID including drugs and supportive interventions (e.g., for supporting mental health or fatigue). Working with patients, doctors and other experts, consensus statements will be developed on: i) therapies for recommended use in the clinical management of Long COVID; ii) therapies to evaluate and iii) therapies not recommended for use. A virtual supportive intervention will be co-produced with patients and health service providers.
 
Data from work packages 1-3 will also be used to inform the development of a clinical trial that will evaluate the remote-delivered intervention produced during the project, and to plan future evaluation of pharmacological and supportive interventions for Long COVID. This will be done under a separate, linked protocol.

--	---

**KEY WORDS:** Long COVID, COVID 19, Symptoms, Quality of life, Patient Reported Outcomes, Therapies

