### 1.0 Background

Coronavirus Disease 2019 (COVID-19), caused by Severe Acute Respiratory Syndrome Coronavirus 2 (SARS CoV-2), is the most significant pandemic since the Spanish Influenza Pandemic of 1918. There have been over 140 million cases worldwide, including over 4.4 million cases in the UK. In the UK, this has resulted in over 460,000 hospital admissions and in excess of 150,000 deaths.

SARS CoV-2 enters human cells using the angiotensin II receptor, which is widely expressed throughout the body. COVID-19 is consequently a multisystem disorder affecting the lungs, heart, gut, kidneys, brain and skin. A wide range of symptoms have been associated with COVID-19 including breathlessness, fatigue, fever, myalgia, “brain fog” and anosmia.

These symptoms resolve within 12 weeks in most affected individuals. However, in up to 10% of individuals, symptoms of COVID-19 persist, sometimes in a relapsing remitting manner. This can have significant impacts on physical and neurocognitive functioning, quality of life and work capability. Those having symptoms lasting beyond 12 weeks are referred to as experiencing post-COVID-19 syndrome (NICE 2019) or more widely known as Long COVID.

The cause of Long COVID is poorly understood. However, there is evidence from other post-viral syndromes that may be applicable to Long COVID. Furthermore, evidence from existing studies on COVID-19 suggest a significant burden of pathophysiological insults and sequelae such as lung scarring, kidney injury, myocarditis and systemic inflammatory states that may promulgate longer term symptoms. There is also a possibility that autoimmune pathways may be triggered by COVID-19, leading to multi-system inflammatory damage.

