### 2.0 Rationale

Approximately 1 in 10 individuals with COVID-19 experience symptoms and impaired quality of life and frequently report experiencing heterogeneous physical and psychological symptoms beyond 12 weeks (“Long COVID”) that can be debilitating. People living with Long COVID have indicated that they are suffering with a

range of symptoms, feel 'abandoned' and 'dismissed' by healthcare providers and receive limited or conflicting advice. The aetiology, pathophysiology and treatments for Long COVID are not well understood, creating an unmet need for the growing number of affected individuals. Although efforts are being made to study Long COVID in hospitalised patients, there is a large unmet need among non-hospitalised individuals. Long COVID may comprise several distinct syndromes yet to be fully characterised.

Existing evidence on Long COVID is based on hospitalised cohorts and non-selected populations that are unlikely to be generalisable to the wider UK population of non-hospitalised individuals. A representative population-based cohort, ideally derived from primary care, is needed to understand the burden of Long COVID, associated disability and impact on work capability. The literature suggests the physical and psychological symptoms of Long COVID are highly diverse and may represent several distinct syndromes. The characterisation of these syndromes using real-world data in combination with patient reported outcomes would aid health services to deliver appropriate interventions to meet these health needs.

The aetiology and risk factors for Long COVID also need further investigation as literature suggests a disproportionately higher prevalence of Long COVID among women, older adults and individuals with specific symptom clusters. One possible explanation for this may relate to differing immunological profiles of individuals who go on to develop Long COVID. For example, older adults with COVID-19 show higher levels of senescent T cells. As these are pro-inflammatory, more likely to be autoimmune and tissue-damaging, their persistence could mediate distinct symptoms in Long COVID among these individuals. Understanding the immunological basis of Long COVID would better enable clinicians to offer targeted therapies.

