### 4.0 Research Outputs and Deliverables

[figure not shown]
1. To establish a population-based representative cohort of 4000 individuals (minimum 2000) with COVID-19, with a minimum of 500 individuals with Long COVID, 500 matched control patients without COVID-19 (control group 1) and 500 matched control patients with COVID-19 but without Long COVID (control group 2). We will capture detailed data on symptoms, quality of life, work capability and objective health measures for individuals with Long COVID and patients in the matched control groups. This will include the development and validation of a new disease-specific PRO of symptom severity and interference for individuals with Long COVID.
2. To develop a new, validated PRO for the measurement of symptom burden in individuals with Long COVID: the Symptom Burden Questionnaire™: Long COVID.

3. To describe distinct Long COVID syndromes and their epidemiology and characterise their immune, inflammatory and proteomic profile, and physical parameters (heart rate intensity, sleep and movement) providing mechanistic understanding of each syndrome and identifying potential therapeutic targets for future evaluation. This will accelerate the identification of potential therapies for Long COVID that are targeted to each syndrome. Based on symptom clusters we will identify up to 200 individuals from the Long COVID cohort, 50 matched control patients without COVID-19, and 50 matched control patients with COVID-19 but without Long COVID to receive bio-sampling and be provided with wearable devices (Garmin Vivosmart4) to measure heart rate, oxygen saturation, step count and sleep quality (BioWear Sub-Study). This will be used in WP2 to deep phenotype Long COVID syndromes.
4. To co-produce a targeted intervention for Long COVID syndromes that can be delivered remotely on a digital platform. This intervention will have patients and carers at the heart of its design and will be based on the best available evidence on Long COVID. It will be designed to be effective, targeted to address symptoms associated with each specific syndrome, acceptable to patients, and scalable.

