#### **Establish a representative population-based cohort of individuals with Long COVID (Objective 1)**

A representative population-based cohort of non-hospitalised individuals with Long COVID will be established using primary care records in the Clinical Practice Research Datalink (CPRD) and recruitment through the Interventional Research Services Platform (IRSP). We will use linked data from the Second-Generation Surveillance PCR-confirmed COVID-19 registry to identify all confirmed COVID-19 patients in CPRD. Using linked Hospital Episode Statistics (HES) data we will identify and exclude hospitalised patients. Further details on each of the data sources is provided (Box 1).

All potential cases will be reported to the Clinical Practice Research Datalink's (CPRD) Interventional Research Services Platform (IRSP). This is a web-based research platform linked to CPRD's anonymised primary care database of coded clinical electronic health care data from approximately 1700 practices across the UK. The platform enables primary care staff to review pre-selected patient lists, confirm eligibility and invite patients to join a study. The selection criteria are applied within the CPRD IRSP, based on the predefined patient selection strategy. A delegated health professional at each practice can subsequently access the pseudonymised patient list, re-identify the patients, and review the clinical record to a set of screening questions. For patients that meet selection criteria, the primary care team will send out an invitation letter informing them about the study and containing key links and information required to enable enrolment onto the study.

Via IRSP, all potential cases will be presented to participating general practices to review their suitability for study recruitment. Those assessed as suitable for study recruitment will be sent an invitation letter to participate in the study. We aim to recruit a minimum of 2000 individuals with COVID-19. Individuals from underrepresented sociodemographic groups (e.g., Black and Minority Ethnic (BAME) and those from areas of high socioeconomic deprivation) will be oversampled. These individuals with COVID-19 (minimum n=2000) will be invited to report symptoms, quality of life and work capability through the Aparito Atom5™ digital platform. Data collected from this cohort of patients with COVID-19 will be used to identify a sub-cohort of patients with long-term symptoms of Long COVID (minimum n=500, aiming for n≥750).

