## 14.0 Sampling

### 14.1 Sample Size

To define Long COVID symptom clusters:

Reliable detection of clustered data via well-chosen combinations of these methods has been shown to require at minimum 20-30 observations per subgroup provided good cluster separation exists (effect size  $\Delta=4$  or over). We expect that with 500 patients in the long Covid cohort we will have power above 80% to detect well-separated clusters comprising at least 5% of the cohort for K=4 to K=6 clusters.

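### The planned minimum of 500 Long COVID cases does not follow from the protocol's own 10% rate, which gives about 200 to 400, and the cluster power statement depends on 500

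*Protocol*

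**What the plan says.** - **Size of the COVID-19 cohort.** The Study Summary gives a "Minimum of 2000 individuals with a diagnosis of COVID-19". Section 4.0 describes a "population-based representative cohort of 4000 individuals (minimum 2000) with COVID-19", and Section 14.2 repeats the aim of 4000.
- **Size of the Long COVID cohort.** The Study Summary gives a "Minimum of 500 individuals with Long COVID identified from the main cohort of individuals with COVID-19". Section 5.0 (Objective 1) gives "minimum n=500, aiming for n≥750".
- **Where the cases come from.** Sections 5.0, 6.1.1 and 6.5.1 (participant identification and recruitment) agree. PCR-positive, non-hospitalised adults are invited, and those who report symptoms at 12 weeks or beyond become the Long COVID cohort. No route recruits people because they have symptoms. The only oversampling is by sociodemographic group (5.0, 14.2).
- **The rate.** Section 1.0 says that "in up to 10% of individuals, symptoms of COVID-19 persist". Section 2.0 says "Approximately 1 in 10 individuals with COVID-19 experience symptoms and impaired quality of life" beyond 12 weeks. No other rate or expected share appears.
- **What is sized on 500.** Section 14.1 says "We expect that with 500 patients in the long Covid cohort we will have power above 80" per cent, for well-separated clusters that make up 5% or more of the cohort, with four to six clusters. It also says that reliable detection needs at least 20 to 30 observations per subgroup.

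**The concern.** The Long COVID cohort is a by-product of the COVID-19 cohort, so its size is the number of participants multiplied by the share with persistent symptoms. The protocol fixes a range for the first and cites one rate for the second, yet their product falls short of the stated minimum even at the full recruitment aim. The paired minimums in the Study Summary (2000 and 500) imply a share of 25%, which is 2.5 times the cited rate, and no reason is given.

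At stake is the sample-size justification for the symptom-cluster objective. It is the only one offered for that objective, and it is conditional on 500 cases. If the yield is nearer the cited rate, the study can find only coarser clusters than the protocol says.

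**Working it through.** **Inputs.** COVID-19 participants N = 2000 (minimum, Study Summary) or 4000 (aim, 4.0 and 14.2). Long COVID share p = 0.10 (1.0 and 2.0). Required cases: 500 (Study Summary) or 750 (5.0). Smallest cluster: 5% of cases. Observations needed per cluster: 20 to 30 (14.1).

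**Step 1: the protocol's cluster statement at its own n.** 0.05 × 500 = 25 people in a 5% cluster, inside the 20 to 30 range. Section 14.1 is therefore consistent with its own rule if there are 500 cases. The figure of 80% power cannot be reproduced, because the protocol gives too few simulation settings, and nothing here depends on it.

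**Step 2: expected cases = N × p.** 2000 × 0.10 = 200 and 4000 × 0.10 = 400. Neither reaches 500. Section 1.0 says up to 10%, so on that sentence these counts are upper expectations.

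**Step 3: share needed = required cases / N.**

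| Required cases | N = 2000 | N = 4000 |
|---|---|---|
| 500 | 500/2000 = 25% | 500/4000 = 12.5% |
| 750 | 750/2000 = 37.5% | 750/4000 = 18.75% |

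**Step 4: sensitivity to the share, which is an assumption.**

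| Share | N = 2000 | N = 4000 |
|---|---|---|
| 10% | 200 | 400 |
| 15% | 300 | 600 |
| 20% | 400 | 800 |
| 25% | 500 | 1000 |

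The minimum of 500 is within reach at 4000 participants with a moderately higher share. At 2000 participants it is not met below 25%.

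**Step 5: consequence for Section 14.1.**

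| Cases | People in a 5% cluster | Cluster share that gives 20 to 30 people |
|---|---|---|
| 200 | 10 | 20/200 = 10% to 30/200 = 15% |
| 400 | 20 | 20/400 = 5% to 30/400 = 7.5% |
| 500 | 25 | 20/500 = 4% to 30/500 = 6% |

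**Step 6: indirect effect on BioWear.** Sections 6.4.1 and 6.5.3 (BioWear sub-cohort) draw 50 from each of four syndromes, up to 200. That is 200/200 = 100% of cases at N = 2000 and 200/400 = 50% at N = 4000, before allowing for consent to contact or unequal clusters.

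**Step 7: Control Group 2.** Participants without Long COVID number 2000 − 200 = 1800 to 4000 − 400 = 3600, against 500 wanted. This pool is not short.

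**The case against.** The strongest reply is that 10% is background narrative and not a planning input. Section 14 never uses it, and Section 2.0 itself doubts that existing evidence carries over to non-hospitalised people in the UK. Participants are self-selected responders classified by self-report, and people with persistent symptoms may respond more readily. The share among responders could well exceed 10%. This stands as a reason why 200 to 400 is not a forecast. It does not supply the missing assumption: the protocol states no higher share, and one that relied on selective response would have to be squared with a representative cohort.

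It is also fair that 4000 is an aim and not a cap. At 10%, 500 cases would need 500/0.10 = 5000 participants, and nothing forbids that number. Nothing plans for it either.

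A reader might draw three stronger conclusions, which the documents do not support:

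- **That all of work package 2 rests on 500.** Only the cluster statement in 14.1 does. BioWear is stated as up to 200 in the Study Summary, 6.4.1 and 6.5.3, and its power table in 14.2 compares 50 with 50. The full-uptake problem arises only at the 2000 floor.
- **That Control Group 2 cannot be filled.** It is drawn from participants without Long COVID, who would be plentiful.
- **That 500 is practically impossible.** A binomial calculation with exactly 10% and 4000 participants gives a probability near 2 in 10 million. That treats an approximate narrative rate as known exactly for a self-selected sample, and at 4000 the required share is only 2.5 points above the cited figure.

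Finally, clustering is described as exploratory (10.1), and a shortfall would show in the baseline data. It would coarsen the results without invalidating a test.

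**Conclusion.** The inconsistency holds. On the protocol's own cited rate, the planned cohort yields about 200 to 400 Long COVID cases against a stated minimum of 500 and an aim of at least 750. The gap closes only with a share of 12.5% to 25% for 500, or 18.75% to 37.5% for 750, and the protocol neither states nor justifies such a share.

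The direct effect is confined to Section 14.1. A 5% cluster falls from 25 people to 10 at the minimum cohort, below the stated floor, or to 20 at the aim, which is the bottom edge of the range. The effect on BioWear is indirect.

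This rests on two assumptions: that the cited rate applies to participants, and that recruitment ends between 2000 and 4000. Either may prove wrong, and the protocol should then say what it assumes instead.

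**What to change.** In the Study Summary and Sections 4.0, 5.0 and 14.1, do one of the following:

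1. State the Long COVID share expected among responders, at least 25% at N = 2000 or 12.5% at N = 4000. Justify it, and explain how it fits with calling the cohort representative. If 750 remains the aim, do the same for 37.5% or 18.75%.
2. Restate the expected count as about 200 to 400, and the smallest detectable cluster as 10 to 15% of 200 or 5 to 7.5% of 400. Add that 50 per syndrome for BioWear may not be reached.

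Under either option, update these figures from the share observed at baseline before the clustering is run.

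The cost is protocol wording and less favourable stated figures. Neither option requires extra participants.

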## STUDY PROTOCOL

Therapies for Long COVID in non-hospitalised individuals

### 1.0 Background

Coronavirus Disease 2019 (COVID-19), caused by Severe Acute Respiratory Syndrome Coronavirus 2 (SARS CoV-2), is the most significant pandemic since the Spanish Influenza Pandemic of 1918. There have been over 140 million cases worldwide, including over 4.4 million cases in the UK. In the UK, this has resulted in over 460,000 hospital admissions and in excess of 150,000 deaths.

SARS CoV-2 enters human cells using the angiotensin II receptor, which is widely expressed throughout the body. COVID-19 is consequently a multisystem disorder affecting the lungs, heart, gut, kidneys, brain and skin. A wide range of symptoms have been associated with COVID-19 including breathlessness, fatigue, fever, myalgia, “brain fog” and anosmia.

These symptoms resolve within 12 weeks in most affected individuals. However, in up to 10% of individuals, symptoms of COVID-19 persist, sometimes in a relapsing remitting manner. This can have significant impacts on physical and neurocognitive functioning, quality of life and work capability. Those having symptoms lasting beyond 12 weeks are referred to as experiencing post-COVID-19 syndrome (NICE 2019) or more widely known as Long COVID.

The cause of Long COVID is poorly understood. However, there is evidence from other post-viral syndromes that may be applicable to Long COVID. Furthermore, evidence from existing studies on COVID-19 suggest a significant burden of pathophysiological insults and sequelae such as lung scarring, kidney injury, myocarditis and systemic inflammatory states that may promulgate longer term symptoms. There is also a possibility that autoimmune pathways may be triggered by COVID-19, leading to multi-system inflammatory damage.

### 2.0 Rationale

Approximately 1 in 10 individuals with COVID-19 experience symptoms and impaired quality of life and frequently report experiencing heterogeneous physical and psychological symptoms beyond 12 weeks (“Long COVID”) that can be debilitating. People living with Long COVID have indicated that they are suffering with a

range of symptoms, feel 'abandoned' and 'dismissed' by healthcare providers and receive limited or conflicting advice. The aetiology, pathophysiology and treatments for Long COVID are not well understood, creating an unmet need for the growing number of affected individuals. Although efforts are being made to study Long COVID in hospitalised patients, there is a large unmet need among non-hospitalised individuals. Long COVID may comprise several distinct syndromes yet to be fully characterised.

Existing evidence on Long COVID is based on hospitalised cohorts and non-selected populations that are unlikely to be generalisable to the wider UK population of non-hospitalised individuals. A representative population-based cohort, ideally derived from primary care, is needed to understand the burden of Long COVID, associated disability and impact on work capability. The literature suggests the physical and psychological symptoms of Long COVID are highly diverse and may represent several distinct syndromes. The characterisation of these syndromes using real-world data in combination with patient reported outcomes would aid health services to deliver appropriate interventions to meet these health needs.

The aetiology and risk factors for Long COVID also need further investigation as literature suggests a disproportionately higher prevalence of Long COVID among women, older adults and individuals with specific symptom clusters. One possible explanation for this may relate to differing immunological profiles of individuals who go on to develop Long COVID. For example, older adults with COVID-19 show higher levels of senescent T cells. As these are pro-inflammatory, more likely to be autoimmune and tissue-damaging, their persistence could mediate distinct symptoms in Long COVID among these individuals. Understanding the immunological basis of Long COVID would better enable clinicians to offer targeted therapies.

There is an urgent need for evidence-based, accessible interventions that are co-produced with patients with lived experience of COVID-19 to better support the growing number of non-hospitalised individuals with Long COVID. We propose to derive treatment recommendations drawing upon existing approaches to the management of post-viral syndromes in addition to a detailed understanding of Long COVID syndromes. There is a pressing need to develop a trial platform that can link symptom, primary care and hospital data with immunological profiling to evaluate interventions for Long COVID in non-hospitalised patients. The Recovery trial and PHOSP-COVID study have demonstrated the strength of platforms where several interventions can be rapidly evaluated in secondary care. However, such an infrastructure is still urgently needed for affected individuals in the wider community.

The proposed research will directly address the patient needs highlighted in the NIHR Evidence Report, by the LongCovidSOS campaign, our patient and public involvement group and patient partners, who have co-designed this study. Our research will characterise the symptoms, health impacts and underlying pathophysiology of Long COVID and define its component syndromes in non-hospitalised individuals. In addition, we will provide tailored resources to support symptom management and nurse-led support for those with the severest symptoms. We will use our findings to co-produce with patients a targeted intervention for Long COVID, tailored to individual patient need.

There is currently a lack of published data relating to the pathogenesis of Long COVID. The University of Birmingham is internationally renowned for leading the exploration of acute COVID-19 immune profiles. The proposed research will build upon this expertise and provide the first immune profile for patients with Long COVID syndromes.

